5.5 Handling of Dropouts and Missing Data

PI [REDACTED]. Please refer to Section 14.3 for the proposed methodology for dealing with missing data in the efficacy analyses of the primary and two key secondary endpoints. PI [REDACTED].

5.5.1 Partial Dates

Where start and stop dates for medications or adverse events are incomplete, imputation rules will be applied.

In the event that the start date of a medication/AE is partial, the following imputation rules will be applied:

- If only day is missing, then the start date will be imputed as the first day of the month. If month and year are the same as the month and year of first dose of study drug then the start date will be imputed as the first dose date.

**Study 111-301 Statistical Analysis Plan**

- If only year is non-missing, then the start date will be imputed as the first day of the year. If year is the same as the year of first dose of study drug then the start date will be imputed as the first dose date.

In the event that the stop date of a medication/AE is partial, the following imputation rules will be applied:

- If only day is missing, then the end date will be imputed as the last day of the month.
- If only year is non-missing, then the end date will be imputed as the last day of the year. If the imputed date is beyond the study completed or discontinued date, the imputed date will be replaced with the study completed or discontinued date.

**Study 111-301 Statistical Analysis Plan****6 SUBJECT DISPOSITION**

At least 110 subjects (55 per treatment group) are planned to be enrolled by approximately 33 sites.

Disposition will be presented based on the FAS. The number of subjects in the FAS, the number of subjects who received study drug, the number of subjects who completed treatment on study drug, and the number of subjects who completed the study will be reported by treatment group.

The total number of subjects who were in the FAS, received study drug, and completed the study (i.e., completed the Week 52 visit) or withdrew prematurely will be summarized by treatment group and depicted by a flowchart in the clinical study report (CSR).

Disposition data will be listed by treatment group, and will indicate the investigator site. In addition, for those subjects who were screen failures, the reason for screen failure will be listed.

**Study 111-301 Statistical Analysis Plan****7 DISCONTINUATION AND COMPLETION**

For subjects who prematurely discontinued from the study, the primary reason for discontinuation will be summarized. A similar summary will be provided for subjects who discontinued study drug.

The number of subjects who completed study drug, and the number of subjects who completed the study will be summarized by treatment group.

All summaries will be based on the FAS, and presented by treatment group and overall.

**Study 111-301 Statistical Analysis Plan****8 PROTOCOL EXEMPTIONS AND DEVIATIONS**

The number and percentage of subjects with any protocol deviation, any major protocol deviation, and any minor protocol deviation will be presented, according to the categories described in the study specific protocol deviation plan. Reasons for major/minor deviations will be summarized.

All summaries will be based on the FAS, and presented by treatment group and overall.

All protocol deviations will be listed by treatment group, and ordered by subject. A separate listing of all major deviations which have been classified as a “Dosing Irregularity” will be provided.

**Study 111-301 Statistical Analysis Plan****9 DEMOGRAPHICS AND BASELINE CHARACTERISTICS**

Demographic and baseline characteristics will be summarized for the FAS, and presented by treatment group and overall.

Demographics will be summarized as:

- Age at Day 1 (years)
- Age at Day 1 (≥ 5 to < 8 , ≥ 8 to < 11 , ≥ 11 to < 15 , ≥ 15 to < 18 years)
- Sex (Male, Female)
- Race (American Indian or Alaska Native, Asian [Japanese/Other], Black or African American, Native Hawaiian or Pacific Islander, White, Multiple, Not Provided Due to Patient Privacy Rules)
- Ethnicity (Hispanic or Latino, Not Hispanic or Latino)

Baseline characteristics will be summarized as:

- Tanner Stage (I, $> I$; Derived as either genitalia (male) or breast (female) Tanner stage)
- Weight (kg)
- Weight Z-Score
- Body Mass Index (kg/m^2)
- Body Mass Index Z-Score

Baseline anthropometric growth measures will be summarized as:

- Annualized Growth Velocity (AGV) (cm/yr)
- Height Z-Score
- Standing Height (cm)
- Sitting Height (cm)
- Head Circumference (cm)
- Arm Span (cm)
- Arm Span to Standing Height Ratio
- Upper Arm Length (cm)
- Lower Arm (Forearm) Length (cm)
- Upper Arm Length to Lower Arm (Forearm) Length Ratio

**Study 111-301 Statistical Analysis Plan**

- Lower Body Length (cm) = Standing Height – Sitting Height
- Upper Leg Length (Thigh) (cm)
- Knee to Heel Length (cm)
- Tibial Length (cm)
- Upper to Lower Body Segment Ratio
- Upper Leg Length (Thigh) to Knee to Heel Length Ratio
- Upper Leg Length (Thigh) to Tibial Length Ratio

In addition to the demographics at baseline, subject's Tanner Stage status will be summarized [n(%)] by visit and presented by treatment group and overall:

- Tanner Stage (I, > I; Derived as either genitalia (male) or breast (female) Tanner stage)
- Pubic hair Tanner Stage (I, II, III, IV, V, Not Done)
- Breast Tanner Stage (Female only) (I, II, III, IV, V, Not Done)
- Genitalia Tanner Stage (Male only) (I, II, III, IV, V, Not Done)

**Study 111-301 Statistical Analysis Plan****10 MEDICAL HISTORY**

Medical history will be solicited from each subject, including all major illnesses, diagnoses, and surgeries that the subject has ever had; any prior or existing medical conditions that might interfere with study participation or safety; and evaluation for knee, thigh, hip or groin pain, or change in gait/activity. All medical history terms will be coded in accordance with MedDRA Version 22 so that each term is assigned a system organ class (SOC) and preferred term (PT).

A predefined list of the achondroplasia-related PTs is provided in a separate project-level document. Prior to the database lock and unblinding of this study, any PTs which have not previously been reported as achondroplasia-related will be identified via medical review, and will be added to this list. The complete list of final terms will be retained in the study file, and documented in the CSR.

All recorded medical history will be summarized on the FAS by system organ class (SOC) and by preferred term (PT), ordered by descending order of frequency of SOC in the overall population. In addition, achondroplasia-related medical history will be summarized separately by SOC and PT in a similar manner.

The number of subjects with abnormal physical exam results at screening will be summarized and listed.

PI

A large rectangular area of the document is redacted with a solid light blue color, covering the text that would follow the "PI" label.

**Study 111-301 Statistical Analysis Plan****11 PRIOR AND CONCOMITANT MEDICATIONS**

Prior and concomitant medications will be summarized for the FAS. For analysis purposes, the following definitions will be used to determine prior and concomitant medications for the entire study period:

- Prior medications: Any medications taken and ended prior to the initial study drug administration date will be considered prior medications.
- Concomitant medications: Any medications taken on or after the initial study drug administration date up to 30 days after discontinuation of study treatment will be considered concomitant medications and included in summary tables. This also includes medications initially taken prior to the initial study drug administration date but continued or ended on or after the initial study drug administration date.

All medications will be included in PI [REDACTED]

Concomitant medications will be summarized for the overall study period, and a separate summary will be provided which includes only those concomitant medications that were initiated on study.

All medications will be coded using the latest version available within BioMarin of the World Health Organization Drug (WHO Drug) dictionary (Version March 2019). Prior and concomitant medication use will be separately summarized by Anatomical Therapeutic Chemical (ATC) medication class (Level 2) and preferred name (i.e., generic medication name). If a medication doesn't have ATC level 2, they are grouped as "ATC Level 2 classification unavailable". A subject reporting the same medication more than once will be counted once when calculating the number and percentage of subjects who received that medication. PI [REDACTED].

Study 111-301 Statistical Analysis Plan

12 COMPLIANCE

Treatment compliance will be calculated based on the study drug preparation and study drug administration records captured in the eCRF, and summarized by treatment group for the safety population.

For each daily injection, the amount of study drug taken will be calculated as the number of units in the syringe pre-injection, minus the number of units remaining in the syringe post-injection. If the number of units in the syringe pre-injection is not captured in the eCRF, then it will be assumed to be the same as the planned dose.

The total amount of study drug taken will be calculated as the amount of study drug taken (units) in the corresponding treatment duration.

The total amount of study drug planned is determined based on the duration of treatment, and the planned units per day.

Percentage compliance for each subject will be derived from the total amount of study drug intake divided by the planned study drug intake, and multiplied by 100:

$$\text{Treatment Compliance (\%)} = \frac{\text{Total Amount of Study Drug Taken (units)}}{\text{Total Amount of Study Drug Planned (units)}} \times 100$$

Treatment compliance will be calculated and summarized by treatment group.

- Compliance with protocol-specified treatment regimen (%)
- Compliance with protocol-specified treatment regimen ($\geq 50\%$, $\geq 60\%$, $\geq 70\%$, $\geq 80\%$, $\geq 90\%$, $\geq 100\%$)

Study 111-301 Statistical Analysis Plan

13 EXTENT OF EXPOSURE TO STUDY DRUG

Dosing information is recorded by subjects (in the paper diary) and also by the site on visit days. In the case of duplicate records with the same date, if the investigator confirms the date, then investigator reported dosing data will be used. All summaries will be based on the safety population, and presented by treatment group.

The day of the first dose of study drug is referred to as Day 1. A missed dose is defined as a calendar day without a dose between the date of Day 1 and date of last dose.

Descriptive statistics will be provided for the following variables:

- Duration of treatment (days)
 - = Date of last dose – Date of first dose + 1
- Total number of doses administered
 - = Number of doses administered between date of Day 1 and date of last dose
- Total number of doses missed
 - = Number of doses missed between date of Day 1 and date of last dose
- Total amount of weight adjusted dose administered (ug/kg)
- Average weight-adjusted daily dose administered (ug/kg/day)

The frequency and percent of subjects will be provided for the following variables, where missed doses are counted between the date of first dose (Day 1) and date of last dose:

- Number of subjects who missed at least one dose
- Number of subjects who missed more than one dose
- Number of subjects who missed more than 5 consecutive doses
- Number of subjects who missed more than 10 consecutive doses

The frequency and percent of all missed doses will be provided for the following variable:

- Reason for missed dose (Site Error, Parent/Caregiver Error, Home Health Error, Adverse Event, Other, Missing).

PI

**Study 111-301 Statistical Analysis Plan****14 EFFICACY EVALUATIONS****14.1 General Approaches for Analyzing Growth Parameters**

All growth parameters assessed by anthropometric measurements are measured at Day 1, Week 13, Week 26, Week 39 and Week 52.

Growth parameters are measured 3 times for each assessment. It is the mean of these 3 assessments that are considered for the summaries and analyses. In the event that all 3 are not available, the mean of the 2, or the individual assessment is taken.

All efficacy endpoints will be assessed using the FAS. In addition, the primary and key secondary endpoints (AGV, height Z-score, and upper to lower body segment ratio) will also be assessed using the PP population.

Estimand formulations are provided for the primary and key secondary endpoints.

Visit windows are applied for all assessments (see Section 5.4) and are used to summarize the growth measures by visit.

Confirmatory statistical testing controlling for the Type I error rate is only performed on the primary analyses for the primary and two key secondary endpoints. Beyond these analyses, there is no control for multiplicity, and p-values from additional analyses on these endpoints or testing of other endpoints are non-confirmatory.

Unless otherwise specified, all growth parameter assessments are considered for inclusion in analyses, including those collected after treatment discontinuation. Therefore, with respect to the intercurrent event of “rescue therapy received”, the assessments will be included for subjects who have received growth hormone or gonadotropin-releasing hormone or had limb lengthening; however the impact of these intercurrent events will be explored in supplementary analyses censoring the data prior to the interventions.

With the exception of AGV (see Section 14.3.1), summary tables for all growth measures including height Z-score, upper to lower body ratio, body proportion ratios, growth measures (see Section 14.5.2), body mass index (BMI), BMI Z-scores and weight Z-scores will include assessments from both the 111-901 study and 111-301 studies at the following time points:

- - 12 Months (111-901)
- - 6 Months (111-901)
- Baseline (111-301)
- Week 26 (111-301)

**Study 111-301 Statistical Analysis Plan**

- Week 52 (111-301).

Each table will include summaries of the absolute measures at each of these time points, and change from baseline at Week 26 and Week 52 (applying visit windows). The tables will summarize data by treatment group. These summaries are on continuous data and will include the number of subjects with assessments, mean, SD, median, 25th and 75th percentile, minimum and maximum.

Results of the statistical analyses will be provided in separate tables, including the least-squares (LS) mean change from baseline at Week 52 for each treatment group, the treatment difference in LS means (calculated as BMN 111 – Placebo), the 95% confidence interval (CI) for the treatment difference, and corresponding 2-sided p-value.

ANCOVA models will be used to determine the treatment difference at 52 weeks. Unless otherwise specified, all models include the following baseline covariates:

- Treatment group
- Stratum: (Male Tanner Stage I, Female Tanner Stage I, Male Tanner Stage >I, Female Tanner Stage >I)
- Age at baseline
- AGV at baseline
- Height Z-score at baseline

Note: If a subject is incorrectly assigned to a stratum at the time of randomization, they will be analyzed according to their actual sex and Tanner stage.

Subgroup analyses will only be performed for the primary analyses of the primary and key secondary endpoints (see Section 14.7).

PI will include the mean values used in analyses and summaries, and will be ordered by treatment group, subject and visit date. An additional PI of standing height will include all assessments (i.e., individual measures and means of the measures).

14.2 Statistical Testing

The overall type I family-wise error rate for testing the primary and key secondary efficacy endpoints will be controlled at the 0.05 significance level using the following 3-step serial gatekeeping multiple comparisons procedure (MCP). Following this MCP, advancement to the next step will only occur if the null hypotheses within a step and the previous step(s) are all rejected at the significance level of 0.05 in favor of BMN 111. If any null hypothesis within a step is not rejected or is rejected but not in favor of BMN 111, the hypothesis tests

Study 111-301 Statistical Analysis Plan

corresponding to all subsequent steps will not be considered confirmatory. All hypothesis tests will be two-sided.

1. The first step will be the test comparing the BMN 111 group to the placebo group for the primary efficacy endpoint, the change from baseline in AGV at Week 52 time point. If the null hypothesis is not rejected (i.e., p-value > 0.05) or is rejected but not in favor of BMN 111, all subsequent statistical tests will not be considered confirmatory. The study is considered positive if the primary test is significant in favor of BMN 111.
2. The second step will be the test comparing the BMN 111 group to the placebo group for the secondary efficacy endpoint, the change from baseline in height Z-score at Week 52 time point. If the null hypothesis is not rejected (i.e., p-value > 0.05) or is rejected but not in favor of BMN 111, the subsequent statistical test will not be considered confirmatory.
3. The third step will be the tests comparing the BMN 111 group to the placebo group for the secondary efficacy endpoint, the change from baseline in upper:lower body segment ratio at Week 52 time point at a significance level of 0.05.

14.3 Primary Efficacy Endpoint

The primary efficacy objective is to evaluate the change from baseline in annualized growth velocity (AGV) at 52 weeks in subjects treated with BMN 111 compared with control subjects in the placebo group.

14.3.1 Annualized Growth Velocity

The primary efficacy endpoint is the change from baseline in AGV at the Week 52 (12-month) time point. For a given interval [Date1, Date2], the AGV is defined as follows:

$$AGV \text{ (cm/yr)} = \frac{\text{Standing Height at Date 2} - \text{Standing Height at Date 1}}{\text{Interval Length (Days)}} \times 365.25$$

where the interval length in days is calculated as Date2 - Date1.

AGV (cm/yr) will be calculated for the following visits:

- Baseline: [Date of last height measurement in study 901 at least 6 months prior to Date of Day 1 visit in study 111-301, Date of Day 1]
- Week 13: [Date of Day 1, Date of Week 13]
- Week 26: [Date of Day 1, Date of Week 26]
- Week 39: [Date of Day 1, Date of Week 39]
- Week 52 (12-month): [Date of Day 1, Date of Week 52]

Study 111-301 Statistical Analysis Plan

The baseline AGV is established in the observational run-in Study 111-901, based on the standing height measurements at least 6 months prior to enrollment to Study 111-301.

The absolute values for AGV at Baseline, Week 26 and Week 52, and change from baseline at Week 26 and Week 52 will be summarized (n, mean, SD, median, 25th and 75th percentile, minimum, maximum) and presented by treatment group.

A box and whisker plot will be provided for AGV (cm/yr) over time (Baseline, Week 26, and Week 52) for each treatment group.

In addition, for the visits at Baseline, Week 26, and Week 52, scatter plots will be provided by sex and treatment group for (1) AGV by age at visit and (2) AGV by Tanner stage (I, II, III, IV, V) (using breast Tanner Stage for females, and genitalia Tanner Stage for males) at visit.

AGV listings will include AGV for all height assessments at all scheduled visits.

14.3.2 Primary Analysis Method

Some aspects of the primary and other analyses for AGV have been revised relative to the protocol, based on interactions with health authorities and blinded data review.

The primary analysis method described below is based on the protocol, but adds criteria necessary for the multiple imputation to be applicable. In case it cannot be applied, an alternative approach for imputing missing assessments is described. Revisions have also been made to the sensitivity analyses defined in the protocol (see Section 14.3.3).

The following primary hypothesis will be tested (two-tailed):

H₀: Difference in mean AGV change from baseline at week 52 between BMN 111 group and the placebo group = 0

H_a: Difference in mean AGV change from baseline at week 52 between BMN 111 group and the placebo group ≠ 0

The estimand formulation is as follows:

- **Population:** FAS
- **Variable:** Change from baseline in AGV at 52 weeks
- **Intercurrent event:** Regardless of whether or not switching to rescue medication had occurred or subjects had discontinued from the study.
- **Population-level summary:** Difference in estimated means between the treatment groups

**Study 111-301 Statistical Analysis Plan**

The estimators for each of the analyses are defined in the relevant sections.

Subjects who discontinue from study drug will be encouraged to remain in the study and their non-missing height measurements will continue to be used in calculating the AGV. In the event that missing data does occur despite all efforts, missing standing height will be imputed based on multiple imputation (MI) with pattern-mixture models (Little 1993; Molenberghs and Kenward 2007, pp. 30, 34-37) implemented in PROC MI of SAS where the missing, unobserved observations of the standing height are assumed to follow a missing not at random (MNAR) mechanism. Each imputation will require at least 5 subjects in the same treatment group who also discontinue treatment prematurely at a similar time point (i.e. no more than a 90 day difference between the last dose dates) and have standing height assessments post treatment discontinuation. This is referred to as off-treatment data, and the data for these subjects with standing height assessments post treatment discontinuation will be used as the reference data in the MNAR statement within PROC MI.

PROC MI will be used to impute missing standing height assessments at Week 52. A regression method will be applied with the fully conditional specification (FCS) which can handle both monotone and non-monotone missing standing height data patterns. The baseline covariates for age, strata, height Z-score and AGV and standing height will be included in the VAR statement along with the post-baseline standing height assessments (including off-treatment assessments) at Week 13, 26, 39 and 52. Missing Week 52 standing height assessments will then be imputed from the subjects with reference data (as defined above) using the missing not at random (MNAR) option.

A fixed seed of 5122019 will be specified to ensure reproducibility of the results and the number of imputations set to 10.

In each of the imputed datasets, missing AGV at Week 52 and the corresponding missing change from baseline in AGV will be calculated using the imputed standing height. Note, missing height Z-scores at Week 52 and the corresponding change from baseline will also be calculated. For each subject whose missing Week 52 value is imputed, the 10 imputed values will be provided in a data listing that will be included in the appendix of the CSR.

Each of the 10 imputed datasets will be analyzed using an ANCOVA model that includes the following fixed-effect terms:

- Treatment group
- Stratum (Male Tanner Stage I, Female Tanner Stage I, Male Tanner Stage >I, Female Tanner Stage >I)

Study 111-301 Statistical Analysis Plan

- Baseline age
- Baseline AGV
- Baseline height Z-score

SAS PROC MIXED will be used to perform the analysis.

PROC MIXED;

CLASS Stratum Treatment;

MODEL Change from baseline in AGV at Week 52 = Baseline_Age Baseline_AGV
Baseline_Height_Z-Score Treatment Stratum;

LSMEANS Treatment / DIFF = control (“Placebo”) CL;

RUN;

For each imputed dataset, PROC MIXED will generate the least-squares (LS) mean change from baseline in AGV at Week 52 for each treatment group, along with the difference in LS means (calculated as BMN 111 – Placebo). PROC MIANALYZE will then be used to combine all of the estimates across the 10 imputed datasets in order to generate an overall estimate for each treatment group, and for the difference between treatment groups, with a 95% confidence interval for the difference and 2-sided p-value. The study will be considered positive if the 2-sided p-value in favor of BMN 111 is <0.05.

If there are less than 5 subjects with reference data as defined above then missing standing height at Week 52 (i.e. Day 365) will be imputed by applying the baseline AGV (cm/yr) to the last available height assessment as follows:

Standing Height at Day 365 =

$$\text{Last Assessed Height} + \frac{\text{AGV at Baseline}}{365.25} \times (365 - \text{Study Day of Last Height Assessment})$$

Based on this imputed standing height, the height z-score and AGV at Week 52 will be calculated. The ANCOVA model will then be applied to AGV at Week 52.

In the event that there are no subjects who discontinue treatment early with a missing assessment at Week 52 the ANCOVA model will be applied without any imputation.

This ANCOVA model analysis without imputation will be repeated on the PP population.

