STUDY DESIGN AND PLAN: This is a phase 3 randomized, double-blind, placebo-controlled, multicenter study to evaluate the effect of BMN 111 on growth velocity in children with ACH. Subjects who are 5 to < 18 years old, with documented ACH confirmed by genetic testing who have been enrolled in Study 111-901 for at least a 6-month period immediately before study entry, and meet all study eligibility criteria, will participate. Approximately 33 clinical centers worldwide will participate in the study.

At least 110 eligible subjects will be stratified based on sex and Tanner stage (Stage I, and > Stage I, with no more than 20% of subjects > Tanner Stage I) at Screening, and randomly assigned in a 1:1 ratio to one of two treatment groups (placebo or BMN 111 at 15µg/kg).

After subjects have completed the treatment period of the study, those in both treatment and control groups may be eligible to receive BMN 111 in the extension study 111-302 after the Week 52/Study Completion Visit.

ANALYSIS POPULATIONS:

The Full Analysis Set (FAS) includes all randomized subjects with a signed informed consent. The FAS will be used for all efficacy analyses. When applicable, additional sensitivity analyses will be carried out for the Per-Protocol (PP) population, defined as a subset of the FAS who are compliant with the protocol and do not have major protocol violations that affect the interpretability of efficacy data.

The Safety Population is a subset of the FAS, and defined as all randomized consented subjects who receive at least one dose of double-blinded BMN 111 or placebo in this study.

The PK Population is defined as all subjects in the FAS randomized to the BMN 111 treatment group, who receive at least one dose of BMN 111 in this study and have at least one evaluable PK concentration.

The Immunogenicity Population is defined as all subjects in the Safety Population who have at least one evaluable immunogenicity sample.

STUDY ENDPOINTS AND ANALYSES:

Primary efficacy endpoint:

The primary efficacy endpoint is the change from baseline in annualized growth velocity (AGV, cm/yr) at week 52.

The primary analysis of the change from baseline in AGV at week 52 will be performed using an ANCOVA model. Missing values will be imputed, either using multiple imputation (MI) techniques or (if there is insufficient data to perform MI) alternative approaches to address missing data. Details of missing data imputation can be found in Section 14.3.2.

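### The 5-reference cut-off for multiple imputation in SAP 14.3.2 is lower than the number of coefficients in the imputation model listed there, and the fallback trigger does not cover the gap

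*SAP*

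**What the plan says.** SAP 14.3.2 imputes missing Week 52 standing height by regression within a fully conditional specification, using the MNAR option of PROC MI. The condition is "Each imputation will require at least 5 subjects in the same treatment group who also discontinue treatment prematurely at a similar time point", where similar means last doses no more than 90 days apart. Such subjects must also "have standing height assessments post treatment discontinuation". The section does not say that one of those heights must be at Week 52.

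The variable list is given in one sentence: "The baseline covariates for age, strata, height Z-score and AGV and standing height will be included in the VAR statement" and, continuing, "along with the post-baseline standing height assessments (including off-treatment assessments) at Week 13, 26, 39 and 52". The data for the fit are restricted: "Missing Week 52 standing height assessments will then be imputed from the subjects with reference data (as defined above"). No reduced predictor set, prior, ridge or rule for dropping variables is stated, and no reason is given for the number 5.

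The fallback opens at the same number: "If there are less than 5 subjects with reference data as defined above then missing standing height at Week 52" is obtained by applying baseline AGV to the last measured height. Elsewhere the wording is more general. The synopsis allows MI "or (if there is insufficient data to perform MI) alternative approaches to address missing data". The opening of 14.3.2 says that the SAP "adds criteria necessary for the multiple imputation to be applicable" and that an alternative is described in case MI cannot be applied. Sections 14.4.1 and 14.4.2 make height Z-score and segment ratio follow whichever route the primary endpoint takes.

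**The concern.** A regression needs more observations than coefficients before its residual variance can be estimated, and a regression-based imputation draws from that variance. If the minimum reference set is smaller than the coefficient count, MI is declared available where it cannot be run as listed.

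In that range the SAP points two ways. The general clauses lead to the fallback; the numerical trigger does not. The routes are different estimators: MI from off-treatment data, pooled over 10 datasets, or one deterministic extrapolation at the child's own pre-treatment velocity. The choice carries through all three tests in the hierarchy (AGV, height Z-score, segment ratio).

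A second gap does not rest on the coefficient count. The 5-subject condition is set for each imputation and depends on each child's stopping date, whereas 14.3.2 (fallback), 14.4.1 and 14.4.2 read as a single switch. Nothing says what happens when one missing child has 5 matches and another does not.

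**Working it through.** **The plan's own figures.** The 5-subject cut-off has no derivation, so there is nothing to reproduce for it. The only computed design figure is the power in SAP 4.5, used here only for its 55 per arm. It reproduces: 1.75 / (2.80 × √(2/55)) = 3.28, which gives 90.1% with a noncentral t on 108 df, against a stated value of about 90%.

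**Step 1: coefficients in the Week 52 model.** Inputs: the variable list in 14.3.2 and the four-level stratum in the same section. All listed variables are taken as predictors, because no narrower set is given.

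- intercept 1
- age 1, height Z-score 1, baseline AGV 1, baseline height 1
- heights at Weeks 13, 26 and 39: 3
- stratum: levels present among the references minus 1, so 0 to 3

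Total: 1 + 4 + 3 = 8 with one stratum present, then 9, 10 and 11 with two, three and four. Entering sex and Tanner stage additively gives 10 when both vary.

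**Step 2: residual df = references minus coefficients, floored at 0.**

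| References with Week 52 height | 1 stratum | 2 strata | 3 strata | 4 strata |
|---|---|---|---|---|
| 5 to 8 | 0 | 0 | 0 | 0 |
| 9 | 1 | 0 | 0 | 0 |
| 10 | 2 | 1 | 0 | 0 |
| 11 | 3 | 2 | 1 | 0 |
| 12 | 4 | 3 | 2 | 1 |

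The result for 5 to 8 does not depend on the strata. With fewer references than coefficients, the coefficients are not unique either.

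**Step 3: chance of zero residual df at 9 to 11.** It is zero at 9 if at least two strata are present, at 10 if at least three are, and at 11 only if all four are. Assume equal sexes and a share s above Tanner I, so the stratum probabilities are (1−s)/2 twice and s/2 twice. At 9 the chance is 1 − 2((1−s)/2)⁹ − 2(s/2)⁹; 10 and 11 follow by inclusion-exclusion. SAP 4.6.2 caps s at 20%; 10% and 5% are assumed.

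| References | s = 20% (cap) | s = 10% | s = 5% |
|---|---|---|---|
| 9 | 99.9% | 99.8% | 99.8% |
| 10 | 89% | 65% | 40% |
| 11 | 45% | 17.5% | 5.5% |

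**Step 4: how often a missing child has 5 or more matches.** The documents give no discontinuation rate, so it is varied. Assumptions: 55 per arm, stopping times uniform over 365 days, and 50% or 80% of discontinuers staying in the study. For a missing child who stopped at day t, matches ~ Binomial(54, d × r × f(t)), where d is the discontinuation rate, r is retention and f(t) = [min(365, t+90) − max(0, t−90)] / 365. The mean of f is 0.432, so at d = 10% the expected number of matches is 54 × 0.10 × 0.5 × 0.432 = 1.17 (1.87 at r = 80%). Averaging the tail probability over t gives the middle column below. The last column is simulated over two-arm trials and counts all trials, not only those in which a child reaches 5 matches.

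| Discontinuation | Missing child has ≥5 matches (r = 50% / 80%) | Trial is mixed: some missing children have ≥5, others <5 (r = 50% / 80%) |
|---|---|---|
| 5% | 0.04% / 0.3% | 0.08% / 0.19% |
| 10% | 0.7% / 4.4% | 3.0% / 6.5% |
| 20% | 9% / 33% | 43% / 63% |

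**Step 5: once 5 matches are reached.** Fewer than 12 are available in 99.8% or more of cases at every rate shown. So when the MI branch opens, the reference set is nearly always in the 5-to-11 range.

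**The case against.** The strongest reply is that 5 is worded as a floor and not as a sufficient number, and that the SAP already has a catch-all. The synopsis and the opening of 14.3.2 send an MI that cannot be applied to an alternative, and 14.3.2 describes only one for missing heights: extrapolation at baseline AGV. On that reading a model with no residual df goes to the fallback and nothing is left to choose. This carries weight. A reader might infer that the sponsor would be free to pick a method after seeing results. The documents do not support that: there is one described alternative, the SAP prevails over the protocol, and the key secondary endpoints are tied to the primary route. What remains is that the operative trigger names only fewer than 5 and contradicts the general clauses from 5 upwards.

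A second reply is that the case is rare. At 5% discontinuation or below that is right, and no passage suggests a rate near 20%. The SAP also encourages subjects who stop drug to stay for assessment.

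A third is that the 11-coefficient count rests on a specification the SAP does not spell out. That stands for 10 and 11 references, where the answer moves with the Tanner share. It does not affect 5 to 8 unless continuous predictors are dropped, and no rule says which.

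The washout sensitivity analysis in 14.3.3 does not use the 5-subject set. It gives a check on the result, but it does not settle the confirmatory rule.

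**Conclusion.** The point holds as a mismatch between a stated threshold and a stated model. With every listed variable as a predictor, the Week 52 regression has no residual df at 5 to 8 references and almost never any at 9. At 10 or 11 it depends on the share above Tanner I: 89% and 45% chance of none at the 20% cap, 40% and 5.5% at a 5% share. The usable set may be smaller still, because a reference need not have a Week 52 height. The unit of the switch, per child or per trial, is also undefined.

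It would be wrong to infer that the primary analysis is likely to fail. With fewer than 5 matches the fallback applies and the mismatch does not arise. Under the assumptions in Step 4 the range is reached very rarely at 5% discontinuation, occasionally at 10%, and becomes material only well above that. This should be corrected because it sits in the confirmatory rule and is cheap to repair. It is not a reason to doubt the design.

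**What to change.** Before unblinding, amend SAP 14.3.2 as follows.

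- Cut the Week 52 imputation model to a few predictors, for example baseline height, last observed height and baseline AGV. That is 4 coefficients with the intercept.
- Set the minimum number of references with an observed Week 52 height clearly above that count. Keeping 5 would leave 1 residual df, which is too thin.
- Use the same number in the MI condition and in the fallback trigger, and refer to it where the synopsis and the opening of 14.3.2 speak of MI not being possible.
- Extend the fallback trigger to cover an imputation model that cannot be fitted.
- State whether the switch is made per child or per trial, and carry that rule into 14.4.1 and 14.4.2.

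Keeping all listed variables and requiring 12 references is possible but weaker: 12/55 is 22% of an arm matched within 90 days, it guarantees only 1 residual df, and it makes MI almost unreachable.

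The cost is SAP wording and minor reprogramming, with no change to trial conduct. The downside is fewer predictors in the imputation model, or MI reached less often.
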